8.1.6. Other Efficacy Measures

The following are potential BPH disease related events not captured as primary or secondary endpoints. They are collected in this study for possible comparison to historical BPH studies and to insure consistency of disease-related adverse event definition:

- Urinary tract infection/urosepsis
- Urinary incontinence (overflow/urge)
- Renal insufficiency

Each of the three 'other efficacy measures' will be summarized by treatment group for number of subjects with at least one post-randomization event across the 2-year period. The crude rate of each measure will be calculated using the Intent-to-Treat population of

each treatment as the denominator; the associated 95% confidence interval will be output. No formal treatment comparisons will be performed.

Data collected in terms of these other efficacy measures will be listed by treatment and subject.

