4. ANALYSIS POPULATIONS

Analysis populations are defined in the following table.

Population	Definition / Criteria	Analyses Evaluated
Intent-To-Treat (ITT)	
 Comprised of all randomized subjects regardless of whether or not treatment was administered This population will be based on the treatment to which the subject was randomized. Any subject who receives a treatment randomization number will be considered to have been randomized. 	
 All.
Per-Protocol (PP)	
 Comprised of all ITT subjects who comply closely with the protocol. Specifically this includes ITT subjects who do not have a deviation which requires exclusion from the PP population. Protocol deviations that would exclude subjects from the PP population are defined in Section 4.1.3 (Deviations which Require Exclusion from the Per-Protocol Population) and Appendix 1 (Exclusions from the Per-Protocol Population). The PP population will not be analyzed if this population comprises more than 80% of the ITT population. 	
 Primary efficacy endpoint only if this population comprises 80% or less of the ITT Population. Details on specific summaries and analyses are outlined in Section 7, Primary Statistical Analyses.

NOTES :

- 'All Enrolled Subjects' is referenced in at least one tabular summary. Enrolled subjects include those who entered placebo run-in phase and/or who were randomized.

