8.1.5. AUR or BPH-Related Surgical Intervention

All AUR and BPH-related surgery events during participation in the study are recorded. Subjects who discontinue from the study are followed for AUR and BPH-related surgery until the 24 month anniversary of randomization. This follow-up is in terms of biannual telephone contacts beginning at the first six month scheduled interval after discontinuation. Analyses will be in terms of events recorded at clinic visits and also collected in the biannual telephone contacts. [Table 4](#) provides an overview of the planned summaries and analyses. A list of planned data displays is in [Appendix 15](#): List of Data Displays.

Time to first AUR or BPH-related surgery will be defined as the number of days from treatment start date to date of the first event (earliest occurring of either AUR or BPH-related surgery) for each subject. Time to first AUR or BPH-related surgery is classified as a secondary efficacy endpoint and will be analyzed in terms of the Intent-to-Treat population.

Censoring will occur at the earliest of the following dates as applicable: the date of prostatectomy, the date of last contact for AUR and surgical intervention, and the date of death. For censoring, 'prostatectomy' will be determined from the eCRF prostatic surgical intervention log using the following codes associated with 'prostatectomy': open, retropubic with or without nerve-sparing, suprapubic, transvesical, perineal, salvage, laparoscopic, laparoscopic assisted. Note this excludes 'partial prostatectomy'.

The 'date of last contact for AUR and surgical intervention assessment' will be assigned as the latest of:

- Date of last treatment-phase visit
- and
- Date of last successful biannual follow-up telephone contact.

Partial dates will be handled as described in Appendix 7, Premature Withdrawals & Handling of Missing Data.

The number of subjects having the first AUR or BPH-related surgery event on or after treatment start will be tabulated by treatment, by the two annual time periods (Month 12 and Month 24), as well as by three month intervals (quarterly) along with the number of subjects at risk during each of these time periods.

Note: Cut-off dates are defined in [Appendix 6](#); definition is repeated here:

Month k Cut-off Date (for k= 3, 6, 9, 12, 15, 18, 21, 24): The maximum of [Month k clinic visit date, Month k lab visit date, Baseline Date + (k * 91/3)].

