8.2.2. Adverse Events

Adverse events (AEs) will be coded using the MedDRA (Medical Dictionary for Regulatory Activities) coding dictionary. As specified in the protocol, disease related events will not be reported as AEs or serious adverse events (SAEs) unless the investigator assesses the event as more severe than expected for the subject's condition. A mapping of the MedDRA primary system organ class and preferred term to which each verbatim term has been coded will be provided in a listing.

Adverse events (AEs) are to be recorded on the electronic case report form (eCRF) from the start of the placebo run-in phase study treatment until the end of the two year study period. Serious AEs (SAEs) are to be recorded over the same time period as non-serious AEs. However, any SAEs assessed **as related** to study participation or related to a GSK concomitant medication, will be recorded from the time a subject consents to participate in the study up to the end of the two year study period. After discontinuation of study treatment, the investigator will monitor all AEs/SAEs that are ongoing until resolution or stabilization of the event or until the subject is lost to follow-up. Investigators are not required to actively seek information on adverse events occurring after the follow-up contact, but may report any adverse event that they believe may be related to investigational product regardless of when the event occurs. Adverse events summaries will include non-serious as well as serious AEs.

Subjects with sexual function related adverse events leading to study withdrawal, will be followed up for up to 6 months after the last dose of study drug using the sexual function Targeted Follow-Up Questionnaire (TFUQ).

If an AE occurs which, in the investigator's judgment, is possibly related to suicidality, a Possible Suicidality-Related Adverse Event (PSRAE) form should be completed by investigators or their designated staff.

Each AE will be categorized into the following periods according to its onset date: pretreatment, post-randomization, on-treatment, post-treatment. These periods are not mutually exclusive and an AE could be categorized into more than one period. The definitions of these categories are provided in [Appendix 8: Adverse Event Time Periods and Special Adverse Event Definitions](#).

Pre-treatment AEs will not be summarized; they will be included in the AE listing specified later in this section.

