11.2. Appendix 2: Time & Events

11.2.1. Protocol Defined Time & Events

Study Procedures	Visit 1a Pre-Screen	Visit 1b** Screening (V1a + 14 days)	Visit 2 Baseline (V1b + 28d ± 4 days)	Visit 3 (Baseline + 13 wks ± 14 days)	Visit 4 (Baseline + 26 wks ± 14 days)	Visit 5 (Baseline + 39 wks ± 14 days)	Visit 6 (Baseline + 52 wks ± 14 days)	Visits 7 - 9 (Years 2, repeat as for V3-V5 of Year 1)	Visit 10 (Baseline + 104 wks ± 14 days)
	Pre-Screen Visit	Start of Placebo run-in	Start of Treatment Phase Baseline (Randomization)	3 months post Randomization (Rand)	6 months post Rand	9 months post Rand	12 months post Rand	15,18 & 21 months post Rand respectively	End of Treatment Phase 24 months post Rand ⁱ
ICF	X								
Inclusion/Exclusion	X	X							
Medical Hx/ Demog/CV Hx/	X								
ECG (12-lead)		X							
Collection of PGx Sample			X						
Safety evaluations									
Concomitant medication	X	X	X	X	X	X	X	⇒	X
Physical Examination ^a		X			X		X	X ^h	X
Vital signs ^b		X	X	X	X	X	X	⇒	X
Haematology/clinical chemistry	X						X		X
HBsAg and Hepatitis C Antibody ^g			X						
Total serum PSA ^c	X				X		X		X
Post-void residual volume (PVR)	X	X***	X		X		X	X ^h	X
AEs ^d		X	X	X	X	X	X	⇒	X
Suicidality (C-SSRS)	X				X		X		X
Efficacy:									
BPH symptoms (IPSS)	X		X	X	X	X	X	⇒	X
Prostate Volume (TRUS)		X					X		X

Study Procedures	Visit 1a Pre-Screen	Visit 1b** Screening (V1a + 14 days)	Visit 2 Baseline (V1b + 28d ± 4 days)	Visit 3 (Baseline + 13 wks ± 14 days)	Visit 4 (Baseline + 26 wks ± 14 days)	Visit 5 (Baseline + 39 wks ± 14 days)	Visit 6 (Baseline + 52 wks ± 14 days)	Visits 7 - 9 (Years 2, repeat as for V3-V5 of Year 1)	Visit 10 (Baseline + 104 wks ± 14 days)
	Pre-Screen Visit	Start of Placebo run-in	Start of Treatment Phase Baseline (Randomization)	3 months post Randomization (Rand)	6 months post Rand	9 months post Rand	12 months post Rand	15,18 & 21 months post Rand respectively	End of Treatment Phase 24 months post Rand ⁱ
Peak Urine Flow (Qmax)	X	X ^{**}	X		X		X	X ^b	X
AUR or BPH-related Surgery			X	X	X	X	⇒	X	X
Pharmacokinetics^j									
Serum PK samples ^j				X	X	X			
Health Outcomes:									
BPH Health Status Q 8 IPSS (BHS)	X		X	X	X	X	X	⇒	X
AUR or BPH-related Surgery Medical Resource Utilisation			X	X	X	X	X	⇒	X
BPH Impact Index (BII)	X		X	X	X	X	X	⇒	X
PAS-SFI		X	X				X		X
Other Efficacy Measures									
UTI /Incontinence / Renal Insufficiency			X	X	X	X	X	⇒	X
Register in RAMOS	X								
Study Medication:									
Call RAMOS/DispenseMeds		X ^e	X ^f	X	X	X	X	⇒	

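### The crude 2-year ITT rates for UTI/urosepsis, incontinence and renal insufficiency count withdrawn men as event-free for time with no described assessment, so they modestly understate 2-year risk

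*SAP*

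**What the plan says.** Section 8.1.6 (Other Efficacy Measures) defines the summary for each of the three measures as the "number of subjects with at least one post-randomization event across the 2-year period". On the denominator it says: "The crude rate of each measure will be calculated using the Intent-to-Treat population of" each treatment. A 95% CI is attached, and the section adds: "No formal treatment comparisons will be performed". One stated purpose of collecting the data is possible comparison with historical BPH studies.

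Section 4 defines the ITT population as "Comprised of all randomized subjects regardless of whether or not treatment was administered".

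The schedule in section 11.2.1 has one row for these events, "UTI /Incontinence / Renal Insufficiency", marked from Visit 2 to Visit 10. Note i adds that the Visit 10 assessments are also done when a subject stops study treatment.

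Follow-up beyond that point appears in section 8.1.5: "Subjects who discontinue from the study are followed for AUR and BPH-related surgery until the 24 month anniversary of randomization". It continues: "This follow-up is in terms of biannual telephone contacts beginning at the first six month scheduled interval after discontinuation". That section says the calls feed the AUR and surgery analyses. Section 8.1.6 names no such source.

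For AUR and surgery the SAP also sets censoring rules and plans Kaplan-Meier, log-rank and Cox analyses. For the three other measures it plans only the crude rate and a listing.

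**The concern.** The summary is framed over two years, but the observation period described for a withdrawn man ends at his last clinic assessment. If he had no event by then, he counts as a man without an event for the whole period. The crude rate then mixes event risk with retention: more or earlier withdrawal lowers it even when the risk is unchanged.

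Two uses are affected. The arm-level rate and its CI are likely to be read as 2-year risk, although they are centred on something lower. Comparison with historical BPH studies is also distorted wherever retention differed between the studies.

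Adverse event reporting does not clearly close the gap. Section 8.2.2 has AEs recorded to the end of the two-year period, but says that "disease related events will not be reported as AEs or serious adverse events (SAEs) unless the investigator assesses the event" as more severe than expected. Section 8.1.6 itself describes the three measures as potentially disease-related, and nothing in the SAP routes AE records into these rates.

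**Working it through.** The SAP states no event rate, withdrawal rate or sample size for these measures, so there is no planned figure to reproduce. What follows is an illustration on stated assumptions.

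**Inputs**
- From the SAP: ITT denominator (sections 4 and 8.1.6), a two-year period (8.1.6), collection at clinic visits only (11.2.1).
- Assumed: true 2-year risk p of 2% to 10%; share withdrawn by Year 2, d, of 10% to 40%; constant hazard; withdrawal times uniform over 0 to 2 years and independent of the event; no events captured after withdrawal.

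**Formulas**
- Hazard per year: h = −ln(1 − p)/2.
- Probability that a withdrawn man's event is seen: m = mean of 1 − exp(−hU) for U uniform on (0, 2) = 1 − p/(−ln(1 − p)).
- Expected crude rate: c = (1 − d)·p + d·m.

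**Worked case, p = 10%, d = 20%**
- −ln(0.9) = 0.10536, so m = 1 − 0.10/0.10536 = 0.0509.
- c = 0.8 × 0.10 + 0.2 × 0.0509 = 0.0902, that is 9.0% against a true 10%.

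**Crude rate by withdrawal share**

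| True risk | d = 10% | d = 20% | d = 30% | d = 40% |
|---|---|---|---|---|
| 2% | 1.90% | 1.80% | 1.70% | 1.60% |
| 5% | 4.75% | 4.50% | 4.26% | 4.01% |
| 10% | 9.51% | 9.02% | 8.53% | 8.04% |

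The relative shortfall is about 5%, 10%, 15% and 20% across the columns, close to d/2, and hardly depends on p. The d/2 rule comes from uniform timing. If every withdrawn man left at the start, c = (1 − d)·p and the shortfall would be d. If all left near Month 24, it would approach zero.

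**Unequal withdrawal, equal true risk**

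| True risk | Withdrawal, arm A vs arm B | Crude rates | Ratio B/A |
|---|---|---|---|
| 5% | 15% vs 25% | 4.63% vs 4.38% | 0.946 |
| 5% | 20% vs 35% | 4.50% vs 4.13% | 0.917 |
| 10% | 15% vs 25% | 9.26% vs 8.77% | 0.95 |
| 10% | 10% vs 30% | 9.51% vs 8.53% | 0.90 |

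**Check of the proposed addition**
- A man observed to time u has a first event with probability 1 − exp(−hu) and contributes expected event-free time (1 − exp(−hu))/h.
- Their ratio is h for every u, so first events per person-year do not depend on d. At p = 10% this is 5.27 per 100 person-years, and at p = 5% it is 2.56, whatever the withdrawal share.
- This rests on the same independence assumption. A Kaplan-Meier estimate at Month 24 also recovers p under it.

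**The case against.** The strongest reply is that the SAP misstates nothing. It calls the statistic a crude rate and names its denominator. It never calls it cumulative incidence. The measures sit outside the primary and secondary endpoints, and no test or claim depends on them. This stands, and it limits the weight of the point.

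Withdrawal is also visible elsewhere: disposition by arm, reason and visit interval (section 6.3, Tables 1.5 and 1.6), exposure by arm (Table 1.31), and subject listings (5.36 to 5.38). A careful reader could see unequal follow-up. These displays do not give the adjusted rate.

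Two stronger readings are tempting but not supported:
- A reader might infer that the telephone calls exclude these events. The SAP does not say so. It describes the calls only for AUR and surgery, and the protocol or call form, not seen here, could add more. If they do, section 8.1.6 should say so.
- A reader might infer that onset dates are certainly available, so that Kaplan-Meier could simply replace the crude rate. The SAP states no onset-date rule for these measures. A record made after Visit 2 could be enough to classify an event as post-randomization. Onset of persistent incontinence may be hard to date.

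Dropping the crude rate could also harm the historical comparison if the earlier studies reported crude rates, which these documents do not show. Finally, an adjusted estimate is unbiased only if withdrawal is unrelated to the event, and men with worsening urinary symptoms may leave because of them.

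**Conclusion.** The point holds in a limited form. On the SAP's own text, the period named in section 8.1.6 is longer than the assessment described for men who withdraw, and no summary of these three measures allows for that. Read as 2-year risk, the crude rate is low by about half the withdrawal share in relative terms: about 5% to 20% for assumed withdrawal of 10% to 40%. At 15% against 25% withdrawal, equal risks of 10% would appear as 9.3% against 8.8%.

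These sizes rest on assumed event and withdrawal rates, constant hazard, uniform independent withdrawal, and no capture of events after withdrawal. A reader might take this as a threat to the trial's efficacy conclusions. It is not: no formal comparison of these measures is planned. It is a modest improvement to descriptive tables, worth making because it is cheap and one stated use of the data is comparison across studies.

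**What to change.** In section 8.1.6 and Tables 2.163 to 2.165:

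1. Keep the crude ITT rate and its 95% CI for historical comparison, labelled *events recorded during clinic follow-up*.
2. Beside it, by arm with a 95% CI, add subjects with a first event per 100 person-years of clinic follow-up. Where onset dates, or the visit of first record, allow, a Month 24 Kaplan-Meier estimate would serve instead.
3. Censor at the last treatment-phase clinic visit or death, not at the telephone-contact date used for AUR and surgery.
4. State that the added estimate assumes withdrawal is unrelated to the event.
5. If the telephone contacts do collect these events, say so in 8.1.6 and set the censoring date to match.

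The methods are already in the SAP: person-year rates for on-treatment AEs (section 8.2.2) and Kaplan-Meier for sexual and breast AEs of special interest (section 8.2.4.3). The cost is a few lines of text and three slightly larger tables. The person-time version, using the visit of first record, should need no new data collection. No primary or secondary analysis changes.

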8.2. Safety Analyses

Safety summaries and analyses are reported in terms of the following data classifications: adverse events, clinical laboratory assessments (haematology and clinical chemistry), total serum prostate specific antigen (PSA), qualitative breast examination, digital rectal examination, vital signs, suicidality, and post void residual volume.

All safety analyses will be performed using the ITT population unless otherwise specified in text or data display shells. Applicable safety analysis and reporting definitions and presentations within “Program Safety Analysis Plan (PSAP, 2016) for GI198745 (dutasteride) and GSK2285985 (fixed dose combination of dutasteride [GI198745] and tamsulosin [GI138525])” are utilized within this RAP, with any deviations noted.

8.2.1. Overview of Adverse Event Tabular Summaries

[Table 5](#) provides an overview of the planned adverse event tabular summaries. A list of planned data displays is in [Appendix 15: List of Data Displays](#).

Reference Section 4 (Analysis Populations) and [Appendix 6](#) (Derived and Transformed Data) for supporting definitions on all below subsections.

Table 5 Overview of Planned Adverse Event Tabular Summaries

Adverse Event Types, High Level							
	Any	Drug-Related	Non-Serious	Serious	Leading to W/D from Study	Perm. D/C of Study Drug	Fatal
By Type	----- 3.1 (6 above categories, excluding Non-serious) -----						
Overall	3.2 3.3 [1] 3.4 [2] 3.13 [3]	3.18 3.19 [1] 3.20 [2]	3.5	3.25 3.26 [1] 3.27 [2]	3.35	3.38	3.33
By 6-Month Onset Period	3.6 3.14 [3]	3.21		3.28			
By Age (<65, ≥65)	3.7	3.22		3.29			
By Age (<75, ≥75)	3.8	3.23		3.30			
By Country	3.9	3.24		3.31			
By Descending Frequency	3.10		3.12	3.11			
By Maximum Intensity	3.15						
Most Common	3.16		3.17				
Adverse Event Types, Two Levels							
	Drug-Related and Serious	Drug-Related and Fatal	Drug-Related and Leading to W/D from Study	Serious and Leading to W/D from Study	Drug-Related and Leading to Perm D/C of Study Drug	Serious and Leading to Perm D/C of Study Drug	
Overall	3.32	3.34	3.36	3.37	3.39	3.40	
Sexual and Breast Adverse Events of Special Interest							
	Altered (Decreased) Libido		Impotence	Ejaculation Disorders	Breast Disorders (includes Enlargement and Tenderness)		
MedDRA	----- 3.41 -----						
Overall (and by baseline characteristics)	3.42		3.43	3.44	3.45, 3.46 [4], 3.47 [5]		
By Type	----- 3.48 -----						
Not Resolved & Leading to Study Withdrawal	Overall	----- 3.49 -----					
	By Type	3.50	3.51	3.52	3.53		
Prostate Cancer Adverse Event of Special Interest							
Prostate Cancer Overall	----- 3.54 -----						
Cardiovascular Adverse Events of Special Interest							
	Acute Coronary Syndrome	Ischemic Cerebro-vascular Events	Cardiac Failure	Ischemic Coronary [6]	Cardiac Arrhythmia	Peripheral Vascular Disease	Cardio-vascular Events
MedDRA	----- 3.55 -----						
Overall	3.56	3.57	3.58	3.59	3.60	3.61	3.62
Infrequent Tier 1 Adverse Events of Special Interest							
MedDRA	----- 3.63 -----						

Notes: Summaries are in terms of 'Starting Post-Randomization' (defined in Appendix 8) unless otherwise noted as [1] – [3]:

1. Starting On-Treatment; defined in Appendix 8.
2. Starting Post-Treatment; defined in Appendix 8.

3. Starting On-Treatment and in terms of 'Study Drug Exposure Basis" in which [Rate] is the number of subjects per 100 person-years of study drug exposure; adverse events for subjects with missing study drug exposure are excluded.
4. Breast Disorders: subcategory Breast Enlargement
5. Breast Disorders: subcategory Breast Tenderness
6. Ischemic Coronary Artery Disorders / Atherosclerosis

8.2.2. Adverse Events

Adverse events (AEs) will be coded using the MedDRA (Medical Dictionary for Regulatory Activities) coding dictionary. As specified in the protocol, disease related events will not be reported as AEs or serious adverse events (SAEs) unless the investigator assesses the event as more severe than expected for the subject's condition. A mapping of the MedDRA primary system organ class and preferred term to which each verbatim term has been coded will be provided in a listing.

Adverse events (AEs) are to be recorded on the electronic case report form (eCRF) from the start of the placebo run-in phase study treatment until the end of the two year study period. Serious AEs (SAEs) are to be recorded over the same time period as non-serious AEs. However, any SAEs assessed **as related** to study participation or related to a GSK concomitant medication, will be recorded from the time a subject consents to participate in the study up to the end of the two year study period. After discontinuation of study treatment, the investigator will monitor all AEs/SAEs that are ongoing until resolution or stabilization of the event or until the subject is lost to follow-up. Investigators are not required to actively seek information on adverse events occurring after the follow-up contact, but may report any adverse event that they believe may be related to investigational product regardless of when the event occurs. Adverse events summaries will include non-serious as well as serious AEs.

Subjects with sexual function related adverse events leading to study withdrawal, will be followed up for up to 6 months after the last dose of study drug using the sexual function Targeted Follow-Up Questionnaire (TFUQ).

If an AE occurs which, in the investigator's judgment, is possibly related to suicidality, a Possible Suicidality-Related Adverse Event (PSRAE) form should be completed by investigators or their designated staff.

Each AE will be categorized into the following periods according to its onset date: pretreatment, post-randomization, on-treatment, post-treatment. These periods are not mutually exclusive and an AE could be categorized into more than one period. The definitions of these categories are provided in [Appendix 8: Adverse Event Time Periods and Special Adverse Event Definitions](#).

Pre-treatment AEs will not be summarized; they will be included in the AE listing specified later in this section.

The number of post-randomization adverse events, the number and the percentage of subjects reporting any post-randomization AE will be summarized by treatment group for the following:

- All AEs
- Drug-related AEs
- Serious AEs
- AEs leading to study drug discontinuation
- AEs leading to withdrawal from study
- Fatal AEs

Comparisons of treatment groups for each of these sets of AEs will be performed using Fisher's Exact Test.

Total number of adverse events reported in the study as well as the number and percentage of subjects reporting at least one AE will be provided for each treatment group. Total number of AEs as well as the number and percentage of subjects reporting each AE will be reported by treatment group, primary system organ class and preferred term. On-treatment and post-treatment AEs will be summarized separately, as well as together as post-randomization AEs. Non-serious post-randomization AEs will be summarized by treatment group. A summary of post-randomization AEs will be provided by treatment group and six month time period of onset (Months 1-6, Months 7-12, Months 13-18, Months 19-24), by treatment group and age group (<65 years, \geq 65 years), by treatment group and age group (<75 years, \geq 75 years), and by treatment group and country.

A summary of post-randomization AEs will be provided by treatment group and preferred term by descending frequency of preferred term (regardless of system organ class). In addition, such summaries will be done for serious post-randomization AEs and also for non-serious post-randomization AEs.

For on-treatment AEs, the event rate per 100 person-years of study drug exposure will be summarized by treatment group, primary system organ class and preferred term overall and by time period (Months 1-6, Months 7-12, Months 13-18, Months 19-24).

A summary of post-randomization AEs will also be provided by treatment group and maximum intensity. If the same AE occurs on multiple occasions in the same subject, the AE with the highest intensity will be presented. Intensity will be categorized as mild, moderate, or severe; a category for missing/not applicable intensity will be included.

The most common AEs (Tier 2 events) are defined as those preferred terms occurring in at least 5% of the subjects within any treatment group (non-rounded). The total number of events as well as the number and percentage of subjects reporting at least one most common AE preferred term starting post-randomization will be provided for each treatment group. The number of events, the number and percentage of subjects reporting the most common AE preferred terms starting post-randomization will be provided by treatment group displayed by decreasing frequency of preferred terms (regardless of primary system organ class). For each of these most common AEs, the percentage of subjects in the treatment groups will be compared using Fisher's exact test. In addition, the percentage of subjects reporting each AE by treatment group along with the corresponding odds ratio and 95% confidence interval for each of the most common AEs

will be displayed in a figure sorted by odds ratio in descending order, by treatment group. The above summary will also be provided for the most common non-serious post-randomization AEs.

Total number of drug-related adverse events as well as the number and percentage of subjects reporting at least one drug-related AE will be provided for each treatment group. Total number of drug-related adverse events as well as the number and percentage of subjects reporting each drug-related AE will be reported by treatment group, primary system organ class and preferred term. On-treatment and post-treatment drug-related AEs will be summarized separately, as well as together as post-randomization drug-related AEs. A summary of post-randomization drug-related AEs will be provided by treatment group and time period (Months 1-6, Months 7-12, Months 13-18, Months 19-24), by treatment group and age group (<65 years, \geq 65 years), by treatment group and age group (<75 years, \geq 75 years) and by treatment group and country.

A listing of all AEs, a listing of AEs by onset period, and a listing of which subjects reported specific AEs will be presented. A listing of Possible Suicidality Related Adverse Event (PSRAE) data will be provided. A listing of the sexual function Targeted Follow-Up Questionnaire (TFUQ) data will be provided.

